#### Depression

To determine the effect of genotype-guided drug therapy on depression symptoms in depression

participants, we will conduct a subset analysis comparing change in depression T-scores from baseline to 3-month follow-up in the Intervention group subset with either CYP2D6 PM or UM or CYP2C19 PM, RM or UM phenotypes to the Control group subset with CYP2D6 PM or UM or CYP2C19 PM, RM, or UM phenotypes. Participants that have other CYP2D6 or CYP2C19 phenotypes will not be included. Pediatric depression T-scores will be transformed to the adult scale using a published crosswalk for a combined analysis. The baseline to 3-month change in depression T-scores of the Intervention CYP2D6 PM/UM or CYP2C19 PM/RM/UM group will be compared to the baseline to 3-month change in depression T-scores of the Control CYP2D6 PM/UM or CYP2C19 PM/RM/UM subgroup using a two-sided two-sample t-test with a type 1 error of 0.049. This primary analysis will be conducted according to a modified intent-to-treat design, with participants analyzed and endpoints attributed according to the treatment arm to which the participants were randomized, regardless of subsequent crossover or post-randomization medical care.

## 10.5 Analysis of the Secondary Endpoints

### All Trials

To determine the effect of genotype-guided drug therapy on overall well-being and the well-being sub-domains (pain interference, physical function, sleep disturbance, social role and activities functioning, fatigue, anxiety, and depression) in acute pain, chronic pain, and depression participants, we will conduct an intent to treat analysis, comparing the well-being (or sub-domain) T-scores from the 6-month follow-up assessments in the Intervention group compared to the control group using a two-sided two-sample t-test or Mann Whitney test, as appropriate, stratified by participant population (acute pain, chronic pain, depression), with a type 1 error of 0.05.

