Primary Endpoint	
Acute Pain: Silverman Integrated Analgesic Assessment (SIA) score (a composite of pain and opioid usage) at 10 days post-surgery in participants who are genetically or pheno-converted CYP2D6 IM or PM
 
Chronic Pain: Pain control, defined as change in the composite pain intensity score from baseline to 3-months in participants who are genetically or pheno-converted CYP2D6 IM or PM
 
Depression: Depression symptom control, defined as change in PROMIS depression 8A scores from baseline to 3-months in genetically or pheno-converted CYP2D6 UM/PM or CYP2C19 UM/RM/PM

Secondary Endpoints	
Acute Pain:
 
 
• Pain intensity at 10 days post-surgery
 
• Opioid usage at 10 days post-surgery
 
• Prescription pain medication misuse score 3 months post-surgery
 
• Mobility score 1-month post-surgery
 
• Opioid persistence 6 months post-surgery
 
 
Chronic Pain:
 
 
• Pain reduction magnitude at 3-month follow-up, relative to baseline
 
• Achievement of clinically significant pain reduction (30%) by 3-month follow-up, relative to baseline
 
• Prescription pain medication misuse score at 3-month follow-up
 
 
Depression:
 
 
• Change in PHQ-8 scores between baseline and 3 months
 
• Achieve 50% reduction in PHQ-8 scores at 3 months, relative to baseline
 
• Medication side effects severity burden at 3 months
 
• Participant medication adherence at 3 months
 
• Achieve remission at 6 months defined as PROMIS depression score <math>\leq 16</math>
 
• Achieve remission at 6 months, defined as PHQ-8 score <math>\leq 4</math>
 
 
All Trials:
 
 
• Overall well-being at 6 months in all randomized participants
 
• Concordance between metabolizer phenotype and prescribed medication
 
• Sub-domains of the PROMIS 43 survey: pain interference, physical function, sleep disturbance, social role and activities functioning, fatigue, anxiety, and depression at 6-month follow-up
 

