- Similarly, the effect of genotype guided antidepressant therapy on all depression secondary endpoints will be compared between the Intervention arm CYP2D6 or CYP2C19 UM, RM or PM subgroup and the Control arm CYP2D6 or CYP2C19 UM, RM, or PM subgroup using either a two-sided t-test, a two-sided Mann Whitney test, or a test of two proportions, as appropriate.
- Additional analyses will include time trends in primary and secondary endpoints, subset analyses, covariate adjustments, and exploratory healthcare utilization and cost effectiveness analyses

All Trials:

- Overall well-being of all Intervention participants will be compared to the overall well-being of all Control participants at 6-month follow-up using ANOVA, adjusting for baseline differences in the two groups
- The effect of genotype guided therapy on concordance between phenotype and prescribed medication will be compared between Intervention and Control participants from the metabolizer phenotypic subgroups specified

	
for each trial's primary endpoint.
 

● Additional analyses will include time trends, subset analyses, and covariate adjustments analyses

--	---

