#### All Trials

*PROMIS 43* – Adults ( $\geq 18$  years of age) will complete a 43-question survey assessing well-being and sub domains: pain interference, physical function, sleep disturbance, social role and activities functioning, fatigue, anxiety, and depression.[32] This survey will be administered to adult participants at baseline, 1-month, 3-months, and 6-months post-surgery (acute pain), or baseline, 1-month, 3-months, and 6-months post return of results (chronic pain, depression).

*PROMIS pediatrics 37* – Pediatric study participants (ages 8-17) will complete a 37-question survey assessing pediatric well-being and sub domains: pain interference, physical function, sleep disturbance, social role and activities functioning, fatigue, anxiety, and depression. This survey will be administered to pediatric participants at baseline, 1-month, 3-months, and 6-months post-surgery (acute pain), or baseline, 1 month, 3 months, and 6 months post return of results (depression).

*Health care utilization* – Survey of the number of significant cost driver health care encounters (e.g. hospitalizations, clinic visits, etc.). This survey will be administered to participants at 10-day, 1-month, 3-months, and 6-months post-surgery (acute pain), or baseline, 1-month, 3-months, and 6-months post return of results (chronic pain, depression).

**Medications** - Participant medications will be collected using patient surveys at baseline and the primary endpoint time points: 10-days for Acute Pain and 3-months for Depression and Chronic pain.

**Productivity loss** – Survey of loss of work the time and pay lost due to the participant's depression or pain. This survey will be administered to participants at 1-month, 3-months, and 6-months post-surgery (acute pain), or 1-month, 3-months, and 6-months post return of results (chronic pain, depression).

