## 10.2 General Statistical Methods

A detailed statistical analysis plan will be developed for each trial (acute pain, chronic pain, and

depression) and contained in a separate document. Prior to analysis, each trial study population details, including the number randomized, in each treatment arm, and lost to follow-up will be described. Baseline participant characteristics will be summarized as means, standard deviations, medians, and 25th, 75th percentiles for continuous variables, and as counts and percentages for categorical variables. Model assumptions will be examined prior to analysis and transformations implemented, if necessary, to more adequately meet the assumptions. Unless otherwise stated, hypotheses will be tested as two-sided with a significance level of 0.05.

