### 11.2 Data Element Definitions

Clinically significant pain reduction: Whether or not the pain reduction score is  $\leq 0.7$ . If the pain reduction score is  $\leq 0.7$ , clinically significant pain reduction is achieved, if pain reduction scores is  $> 0.7$ , clinically significant pain reduction is not achieved.

Depression symptom control: The change in the PROMIS Emotional Distress - Depression 8b or PROIMIS pediatric Depression 8a survey depression score from baseline to time t.

Depression remission: A. Whether or not the summed raw PROMIS emotional distress depression 8b survey responses are  $\leq 16$ , which is equivalent to the participant responding “rarely” or “never” to most or all of the PROMIS emotional distress - depression 8b survey questions. B. Whether or not the PHQ-8 scores are  $\leq 4$ , which is equivalent to depression severity being none-mild.

Depression (PHQ-8) score: The sum of the responses to the PHQ-8 survey, range from 0 to 24.

Depression (T) score: The T-score converted summed responses to the PROMIS emotional distress depression 8b survey. The T-score conversion is centered around 50 with standard deviation of 10.

Depression severity: The depression score converted to depression severity (none, mild, moderate, severe) based on the scoring guide for the PROMIS emotional distress depression 8b survey.

Medication adherence: The scored responses to the Voils Medication Adherence survey.

Medication concordance: Whether or not the medication the participant is prescribed after the intervention is concordant with the participants CYP2D6 and, for the depression trial, CYP2C19 phenotype.

Medication side effects severity burden: (Depression only) The sum of the scored severity (none = 0, mild = 1, moderate = 2, severe = 3) for common SSRI side effects.

Opioid misuse score: The T-score converted summed responses to the PROMIS prescription medication misuse 7a survey. The T-score conversion is centered around 50 with standard deviation of 10.

Opioid persistence: Defined as  $\geq 1$  opioid prescription refill between 90 days and 180 days after the surgical procedure.

Opioid usage: The average daily morphine equivalents in mg (MED) in past 7 days. MEDs will be calculated using data from the opioid usage survey.

Overall well-being: Defined as the T-score converted summed responses to the PROMIS 43/PROMIS 37 pediatrics survey. The T-score conversion is centered around 50 with standard deviation of 10.

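### Six-month overall well-being has two different analyses, one baseline-adjusted (synopsis) and one not (section 10.5), and section 10.5 leaves out the collected baseline score

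*Combined protocol and SAP*

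**What the plan says.** The synopsis lists the endpoint, for all three trials, as "Overall well-being at 6 months in all randomized participants". Its Statistical Analyses entry for All Trials compares the arms "at 6-month follow-up using ANOVA, adjusting for baseline differences in the two groups". It does not say which baseline variables are meant, and the sentence covers overall well-being only.

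Section 10.5, All Trials, analyses the same endpoint and its seven sub-domains by intention to treat. It compares "T-scores from the 6-month follow-up assessments in the Intervention group compared to the control group using a two-sided two-sample t-test" or a Mann-Whitney test, "stratified by participant population (acute pain, chronic pain, depression), with a type 1 error of 0.05". It has no baseline term and no change score.

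The baseline score exists. Section 11.2 defines overall well-being as follows: "Defined as the T-score converted summed responses to the PROMIS 43/PROMIS 37 pediatrics survey". Section 7.3 says of the adult questionnaire: "This survey will be administered to adult participants at baseline, 1-month, 3-months, and 6-months post-surgery (acute pain"; it sets the matching schedule for the other two trials and for the pediatric form. Table 8 shows the questionnaire at baseline in all three trials.

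**The concern.** One endpoint, at one time point and in one population, has two prescribed tests that can give different p-values. Section 10.9 makes no multiplicity adjustment for secondary endpoints. It reports nominal p-values and relies on prespecified outcomes and consistency across endpoints. That reliance is weaker when the test itself can be chosen after the results are known, and the option of a t-test or Mann-Whitney test in section 10.5 widens the choice.

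The second issue is efficiency. Well-being at 6 months is likely to correlate with well-being at entry. A comparison of 6-month scores alone leaves that variation in the error term, although the trials pay to collect the baseline score. This applies to overall well-being and to all seven sub-domains.

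**Working it through.** **1. Do the two texts conflict?**

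| | Synopsis, All Trials | Section 10.5, All Trials |
|---|---|---|
| Population | all Intervention v all Control | intention to treat, by arm |
| Time | 6 months | 6 months |
| Overall well-being | ANOVA with baseline adjustment, covariates unnamed | t-test or Mann-Whitney, no baseline term |
| Seven sub-domains | no test named | t-test or Mann-Whitney, no baseline term |

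The conflict is in the overall well-being row: one comparison in each trial. Both texts are current; neither is in the amendment log. The stratification in section 10.5 separates the three trial populations and is not a baseline adjustment.

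**2. Does another section settle it?** The covariate-adjusted mixed models in section 10.6 cover pain, opioid usage, misuse, mobility and depression symptom scores in the actionable subgroups. Well-being is not listed. The synopsis adds "Additional analyses will include time trends, subset analyses, and covariate adjustments analyses", with no model specified. The cost-utility analysis in section 10.6 does adjust for baseline utility derived from the PROMIS-43, so this questionnaire's baseline is used there but not in section 10.5.

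**3. Plan figures.** The plan gives no power, effect size or sample size for well-being, so there is nothing to reproduce for this endpoint. The primary calculations behind Table 9 do reproduce: at alpha 0.049 two-sided and 90% power, the exact t solutions for effect sizes 0.375, 0.40 and 0.28 are 151.2, 133.02 and 270.4 per arm, which round up to the stated 152, 134 and 271. Dividing by the assumed actionable shares gives the completers per arm: 152/0.18 = 844.4, so 845; 134/0.30 = 446.7, so 447; 271/0.40 = 677.5, so 678.

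**4. What the baseline score is worth.** With baseline to 6-month correlation r, the variance of the ANCOVA arm difference is (1 − r²) times that of the unadjusted difference, and the equivalent sample size is 1/(1 − r²). The documents give no r, so 0.3 to 0.7 is an assumption.

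- r = 0.3: variance ratio 1 − 0.09 = 0.91; 1/0.91 = 1.10
- r = 0.5: variance ratio 1 − 0.25 = 0.75; 1/0.75 = 1.33
- r = 0.7: variance ratio 1 − 0.49 = 0.51; 1/0.51 = 1.96

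**5. On the T-score scale.** Take SD 10 (section 11.2), alpha 0.05 two-sided, 90% power and the Table 9 completers. The detectable difference is (1.960 + 1.282) × 10 × √(2/n), multiplied by √(1 − r²) when adjusted.

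| Trial | n per arm | No baseline term | r = 0.3 | r = 0.5 | r = 0.7 |
|---|---|---|---|---|---|
| Acute pain | 845 | 1.58 | 1.50 | 1.37 | 1.13 |
| Chronic pain | 447 | 2.17 | 2.07 | 1.88 | 1.55 |
| Depression | 678 | 1.76 | 1.68 | 1.52 | 1.26 |

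For an illustrative 2-point difference in chronic pain, power is 84.8% with no baseline term, and 88.0%, 93.2% and 98.7% at r = 0.3, 0.5 and 0.7.

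**The case against.** The unadjusted test is valid. The population is everyone randomised, so omitting baseline costs precision and introduces no bias. Unadjusted two-group tests are also the plan's usual choice for secondary endpoints, including acute pain mobility and misuse, which have a baseline measure too. This stands, and it limits the point to precision and prespecification.

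Section 10.2 says "A detailed statistical analysis plan will be developed for each trial". Those documents are not among the ones reviewed and may resolve the matter. Even so, a later plan would have to depart from one of the two current texts. Section 10.9's cautious stance on secondary endpoints limits the harm of a free choice of test without removing it.

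The gain depends on an assumed correlation. At 0.3 it is small. It may be smaller in acute pain than in the other trials, because section 7.2 takes that baseline before surgery. The variance formula also does not describe the Mann-Whitney option.

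Three stronger readings are tempting:

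- A reader might infer that all eight comparisons in each trial are in conflict. The synopsis sentence names overall well-being only, so the sub-domains have one stated test.
- A reader might infer that adjustment is worth at least a third more participants. That requires r of 0.5 or more, which the documents do not support.
- A reader might infer that the endpoint is underpowered because most participants are not actionable. The plan sets no target difference for well-being. Normal and ultra-rapid metabolisers in the pain trials also receive recommendations (Table 5), and the depression share may reach 60% (Table 9).

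**Conclusion.** The inconsistency is real and unresolved in the documents: 6-month overall well-being has a baseline-adjusted analysis in the synopsis and an unadjusted one in section 10.5, in each of the three trials. The sub-domains are not in conflict, but their single test leaves out a baseline score that is already collected.

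The consequence is a choice of test open after the data are seen, plus a loss of precision. Over assumed correlations of 0.3 to 0.7, adjustment would lower the variance of the arm difference by about 9% to 49%. The detectable differences above also assume SD 10 and Table 9 completers. The synopsis randomisation targets (about 1730, 985 and 1540) would shift them a little but leave the variance ratio unchanged.

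This should be corrected before analysis. It concerns a secondary endpoint and does not threaten the validity of either test.

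**What to change.** State one analysis in both the synopsis and section 10.5. Within each trial, in all randomised participants, fit a linear model (ANCOVA) of the 6-month T-score on arm, the same scale's baseline T-score and the randomisation factors in section 4.1:

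- site, or the clinic unit actually used for randomisation, with small units pooled or fitted as a random effect (section 4.1 allows either unit, and the synopsis expects 60-80 clinics);
- pediatric or adult, in acute pain and depression;
- depression status, in chronic pain.

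Use this model for overall well-being and the seven sub-domains. Delete the synopsis wording on baseline differences between the groups, since the covariates are then fixed in advance. Keep the unadjusted t-test or Mann-Whitney test as a sensitivity analysis, which also covers doubt about model assumptions.

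The cost is a short rewrite of two places and a decision on the site or clinic unit. No new data, visits or participants are needed.

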### Acute Pain

The effect of genotype-guided opioid therapy on secondary endpoints pain intensity, opioid usage, opioid misuse score, and mobility score will be assessed by comparing the Intervention group subset with CYP2D6 IM or PM phenotypes to the Control group subset with CYP2D6 IM or PM phenotypes using a two-sided two-sample t-test or Mann Whitney test, as appropriate, with a type 1 error of 0.05. The effect of genotype guided opioid therapy on the secondary endpoint opioid persistence will be assessed by comparing the Intervention group subset with CYP2D6 IM or PM phenotypes the Control group subset with CYP2D6 IM or PM phenotypes using a test of two-proportions with an alpha of 0.05. Participants with other CYP2D6 phenotypes will not be included in these analyses.

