##### Acute pain

1. Pain intensity at 10 days post-surgery
2. Opioid usage at 10 days post-surgery
3. Prescription pain medication misuse score at 3-months post-surgery
4. Mobility at 1-month post-surgery
5. Opioid persistence 6 months post-surgery

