#### **4.1 Randomization**

After participants provide informed consent/assent, participants will be randomized in a 1:1 allocation to the Intervention (i.e. immediate PGx testing and genotype-guided opioid or SSRI therapy with clinical decision support) and Control (i.e. usual care with delayed PGx testing) arms. Randomization will be stratified by trial and site or clinic with a random block size within each site or clinic. We anticipate variability in patient populations between recruiting sites or clinics and aim to balance the intervention assignments within the site or clinic unit. Additionally, the randomization for the chronic pain trial will be stratified by presence/absence of depression, and the randomization for the acute pain and depression trials will be stratified by pediatric/adult.

The randomization scheme will be generated by an unblinded statistician. Randomization assignments will be generated in real time in REDCap at the Coordinating Center.

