## 5. STUDY POPULATION

### 5.1 Inclusion Criteria

#### Acute Pain

- Age  $\geq$  8 years
- English speaking or Spanish speaking
- Elective/planned surgery types with planned or anticipated to be treated with tramadol, hydrocodone, or codeine pain management at an enrolling site, which may include orthopedic surgeries(e.g. arthroplasty, spine, etc.), open abdominal surgery, or cardiothoracic surgery and others

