**Acute Pain:**

**PROMIS Numeric Rating Scale - Pain Intensity** - An 11-point numeric scale ranging from 0 (no pain) to 10 (worst possible pain) for average pain. This survey will be administered to all participants at baseline, 10 days, 1-month, 3-months, and 6-months post-surgery.

**PROMIS pain intensity scale** – A participant completed 3-question survey of average pain over the last 7 days, worst pain over the last 7 days, and current pain. Each question is on a 1-5 integer scale, the higher the value, the more intense the pain. This survey will be administered to all participants at baseline, 10 days, 1-month, 3-months, and 6-months post-surgery.

**Opioid consumption questionnaire** – A participant completed survey of pain prescription medication consumption, including the type of opioid pain medication, number of pills dispensed, if a refill has been obtained, and the number of pills left for each opioid pain medication selected. This survey will be administered to all participants at 10 days and 1-month post-surgery.

**PROMIS prescription medication mis-use scale** - A participant completed survey of prescription medication misuse over the past 3 months. The survey is comprised of 7 questions on a 5-point ordinal scale of never/rarely/sometimes/frequently/almost always or not at all/a little bit/somewhat/quite a bit/very much[33]. This survey will be administered at baseline, 3-months, and 6-months post-surgery.

**PROMIS Item Bank v2.0 Mobility** – A participant completed survey of the participant's level of difficulty in completing different physical activities such as standing unassisted, walking, and sprinting or activities that their health currently limits. The survey is comprised of 15 questions, each answered on a 5-point scale ranging from without difficulty to unable to do, or not at all through cannot do[34]. This survey will be administered at baseline, 10 days, 1-month, 3-months, and 6-months post-surgery to the adult participants.

**PROMIS Pediatric Mobility – Short Form 8a** – A participant completed 8 item survey of difficulty in completing different physical activities such as getting up from the floor, standing on tiptoes, and ability to do sports and exercises that their peers can complete [35]. The survey will be administered at baseline, 10 days, 1-month, 3-months, and 6-months post-surgery to the pediatric participants.

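### The acute pain mobility test pools different adult and pediatric forms with no defined score and no age-stratum term; with T-scores the cost is small, and the remedy is free

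*Combined protocol and SAP*

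**What the plan says.** Mobility is a named secondary endpoint of the acute pain trial (Section 3.2): "Mobility at 1-month post-surgery". Section 5.1 admits participants from age 8, so the trial takes both children and adults.

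Section 7.3 assigns the instrument by age. For the adult form: "The survey is comprised of 15 questions, each answered on a 5-point scale ranging from without difficulty to unable to do". For the pediatric form: "A participant completed 8 item survey of difficulty in completing different physical activities".

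Section 10.5 treats the result as one score: the "secondary endpoints pain intensity, opioid usage, opioid misuse score, and mobility score will be assessed by comparing the Intervention group subset" with the control subset, both restricted to the actionable phenotypes, "using a two-sided two-sample t-test or Mann Whitney test, as appropriate, with a type 1 error of 0.05". No stratum or covariate is named.

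Section 11.2 defines the depression, opioid misuse and well-being scores as T-scores and pain intensity as a mean of three items. It has no entry for mobility.

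Two other places bear on the point. Section 4.1 states that "the randomization for the acute pain and depression trials will be stratified by pediatric/adult". Section 10.4, for the depression trial, states: "Pediatric depression T-scores will be transformed to the adult scale using a published crosswalk for a combined analysis". Nothing comparable is stated for mobility.

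**The concern.** Two forms of different length and content feed one comparison, and the plan does not say how either is scored or how they are put together. Elsewhere the plan recognises that pediatric and adult T-scores need a link before they are analysed jointly, so the silence on mobility stands out.

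An unstratified two-sample test counts any systematic difference between the forms as person-to-person variation. In a t-test it enlarges the error variance; in a Mann-Whitney test it enters the ranks. Either way some precision is lost, and the pooled arm difference has no clear unit.

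The trial already randomizes within the pediatric/adult stratum, so the variable that would remove this noise is on file for every participant and is simply not used.

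**Working it through.** **1. The plan's own figure.** Section 10.1 gives 152 per arm for 90% power at a standardized effect of 0.375 and two-sided alpha 0.049. The noncentral t distribution gives 90.15% at 152 per arm and 89.96% at 151, so 152 reproduces. This calculation is for the SIA primary endpoint. The plan has no power statement for mobility, and 0.375 and 152 are borrowed below only as a scale. At the secondary-endpoint alpha of 0.05 they give 90.3%.

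**2. Inputs that the documents do not give (assumed).**
- Pediatric share p of the analysed subset: 5%, 10% or 20%.
- Scoring: each form's own T-score, with SD 10.
- Gap between the two calibrations: 5 points, which is g = 0.5 SD.

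**3. Formula.** With the same share of children expected in each arm, pooling multiplies the within-form variance by

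1 + p(1 − p)g².

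Efficiency relative to a stratified test is the reciprocal, and the effective standardized effect is 0.375 / √[1 + p(1 − p)g²].

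**4. Results under T-scores** (noncentral t, 152 per arm, alpha 0.05; 90.3% with a stratum term).

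| Children | Variance factor | Efficiency | Power, unstratified |
|---|---|---|---|
| 5% | 1 + 0.0475 × 0.25 = 1.012 | 0.988 | 90.0% |
| 10% | 1 + 0.09 × 0.25 = 1.023 | 0.978 | 89.7% |
| 20% | 1 + 0.16 × 0.25 = 1.040 | 0.962 | 89.2% |

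The largest loss is 90.3 − 89.2 = 1.1 percentage points.

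**5. Sensitivity to the gap.** Doubling the gap to 1 SD (10 points) gives 89.1%, 87.9% and 85.9% for the same shares, by the normal approximation, against 90.5% with no gap.

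**6. Validity.** A simulation of 5,000 runs per setting was made with p = 5% and 10% at a gap of 1 SD, and p = 10% and 20% at a gap of 2 SD. The unstratified t-test rejected a true null in 4.7% to 5.6% of runs, which is not inflation beyond simulation error. The issue is precision, not error rate.

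**7. Item means instead of T-scores.** Suppose adults and children both sit at 70% of their form's range, with five-level items on both forms (assumed for the pediatric form). The adult sum is 15 + 0.7 × 60 = 57 and the pediatric sum is 8 + 0.7 × 32 = 30.4. The item means are 57/15 = 3.8 and 30.4/8 = 3.8. The gap is zero and nothing is lost.

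**The case against.** The case for leaving the plan alone has real force.

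- Randomization is stratified by pediatric/adult, so the arms are balanced by form in expectation and the test is valid. This stands, and it rules out any claim of bias.
- Every continuous PROMIS score that Section 11.2 does define is a T-score or an item mean. If mobility follows suit, the loss is small or nil. This also stands.
- The share of children is unknown. The example procedures (arthroplasty, spine, open abdominal, cardiothoracic) and the arthroplasty pilot point towards a mostly adult sample, so 20% may be too high.
- Section 10.6 lists pediatric and adult subgroups and a time-trend model for mobility that may include age. Both are exploratory and leave the Section 10.5 test unchanged.
- Section 10.2 defers detail to a separate SAP for each trial, which is not among the documents reviewed. It may define the score and a stratum term. The point is therefore limited to what Sections 10 and 11.2 state.

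A reader might infer a much larger loss by supposing that raw sums of the two forms are pooled. With the 57 and 30.4 above and SDs of 20% of range (12 and 6.4), the between-form variance is p(1 − p) × 26.6². Efficiency would then be 0.805, 0.677 and 0.522, and power 83%, 77% and 65%, for 5%, 10% and 20% children. The documents do not support that reading: nowhere does the plan say that raw mobility sums will be analysed, and doing so would depart from its own convention. A raw PROMIS sum appears in Section 11.2 only as the depression remission cut-off.

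**Conclusion.** The point holds as a minor one. Section 10.5 tests a mobility score that Section 11.2 does not define, pools two different forms, and leaves out a stratum that the trial randomizes by. There is no bias in expectation and no inflation of type I error, and the SIA primary analysis is untouched. The cost is a pooled difference without a clear unit, plus some precision: about 1% to 4% of efficiency, or roughly 0.3 to 1.1 points of power. That range assumes T-scoring, a 5-point calibration gap, 5% to 20% children, and an effect size and sample borrowed from the primary endpoint. The loss becomes large only with pooled raw sums or with both a wide gap and many children, neither of which the documents state.

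A reader might also infer from the depression trial that a mobility crosswalk is required. It is not: once arms are compared within age group, the two forms need not share a scale for the test to be efficient. The documents do not show whether such a crosswalk exists.

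**What to change.** - In Section 11.2, define mobility as each form's own T-score, with the form determined by age group.
- In Section 10.5, compare arms with a pediatric/adult stratum term: a linear model with arm and stratum, or a van Elteren test if ranks are used.
- Add the same term to the PROMIS 43 / pediatric 37 well-being and sub-domain comparisons in the acute pain and depression trials. Section 10.5 already specifies T-scores there, but stratifies only by trial population. The chronic pain trial enrols adults only and needs no change. No loss was calculated for these comparisons.
- If the separate SAP already contains these rules, bring Sections 10.5 and 11.2 into line with it.

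The cost is wording only. The stratum is already recorded at randomization, and no data collection, sample size or alpha changes.
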